5.0 Study Procedures

5.1 Study Design

Overview

This study employs an open-label, pre-post design. There is NO randomization and all interested and eligible couples will be scheduled to complete all study activities described below. Study activities can be completed in as little as 1-month but can take up to 3 months from baseline to finish depending on participant scheduling difficulties. To address public health concerns during the COVID-19 outbreak, the protocol has been designed so that all sessions can occur in person or remotely. This way, participants with relationship distress who are seeking support can still engage in the program without increasing risk to health (e.g., unnecessary exposure to infection during period of containment protocols) or increasing discomfort/distress (e.g., anxiety about exposure even after outbreak is resolved). Remote options include completing a session by VA Video Connect application (VVC) or by phone. VVC uses encryption to provide a secure and private session and is routinely used in VHA behavioral health to deliver the experience of a face-to-face intervention to Veterans and their families at home. Phone calls will be used for when couples have difficulties using the VVC service (e.g., VVC connectivity issues; couples without access to a video-enabled device). For the remainder of the study procedures section, we will use the term "remote" to refer to participating in the session either by phone/VVC, providing information specific to one approach when applicable.

Baseline

After both partners are confirmed eligible and interested in the study through the screening process (see section 5.2), they will be scheduled for separate 2-hour baseline sessions where each partner will complete their paper consents (*Doc#11*), HIPAA authorization (*Doc#8*) study measures (*Doc#15*), and interviews assessing intimate partner violence and suicide risk (*Doc#16*). Non-Veteran partners will also be provided with the notification of Privacy Practices and will sign the Acknowledgment of the Notification of Privacy Practices at this session (*Doc#30*).

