Protections to minimize suicide risk. This study will provide participants with a formal assessment of suicide risk. Therefore, participation in the study would lead to providing more information about a patient's suicide risk and equip patients with additional precautions than would otherwise be available. If participants screen positive for suicidal ideation or researchers become aware that a participant might be thinking about suicide, researchers will assess risk using the P4 screener, a screening form that was developed to help non-mental health practitioners and researchers assess for suicide risk. Note that if researchers become aware that a participant is thinking about suicide during a joint treatment session, this participant will be taken to a private location to continue the assessment. This will improve the reliability of assessment, protect participant confidentiality, and allow for collaborative risk management process should the need arise. All study staff will receive adequate training in suicidal ideation and risk assessment, and all work will be supervised by the Drs. [name] or [name], both are licensed clinicians who have supervised studies of high-risk populations.

If the participant is determined to be at higher risk, an appropriate safety plan will be initiated. Such plans will depend on the setting (i.e., outpatient or telephone assessment) but may include a walk to the ED, warm transfer to the National Veterans Crisis Line ([name]), an in-person appointment with a local provider, or emergency services such as 911, among other options.

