If study staff are concerned about risk during a VVC session (e.g., VVC baseline; VVC treatment sessions; VVC follow-up assessment), we will enact risk management procedures consistent with national telehealth guidelines. Specifically, these guidelines require that study staff will verify and/or update necessary patient information at the beginning of each telehealth session (i.e., current location, patient's phone number; contact information of emergency support if available; and local emergency # if different than 911). This will allow the interviewer to both develop technology contingencies with the couple (e.g., in case of poor connection) or respond to physical or mental health emergencies. The VVC service includes a specific enhanced-911 service (E911) that is prepared to respond to medical emergencies or mental health emergencies occurring during telehealth sessions. If patients are determined to be at imminent risk for suicide during a session, the interviewer will utilize this E911 service, which has established procedures for locating callers and initiating rescues in collaboration with local emergency services. E911 also has mental health responders trained to respond to suicidal crises. Interviewers will try to elicit agreement for necessary services and will always inform patients that they are seeking additional care if the patient refuses to cooperate. We will disclose to the responder any information that bears directly on risk (e.g., level of risk, suicide plan, access to a weapon, prior attempts, etc.). As with in-person sessions, study clinical staff

will be accessible to provide guidance to research staff and interventionists about appropriate risk determination as well as treatment.

Protection against IPV risk. Our IPV risk management procedure is consistent with VA guidance for couples therapy (which advises that the best time to initially screen for IPV is during individual in-person sessions and then every subsequent contact) IPV Assistance Program guidelines (which takes a person-centered approach to deciding on the next course of action). Accordingly, violence will first be systematically assessed during the Baselines, which are conducted separately and maximize each partner's assurance of privacy and confidentiality. After that, all sessions will contain the 1-item self-report IPV screen used as a default in session packets in VA couples therapies.

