5.4 Inclusion/Exclusion Criteria

List of criteria for inclusion

- 1) Both partners must be age 18 or over
- 2) Both partners must demonstrate sufficient knowledge of English and cognitive capacity to understand the study through comprehension of consent questions
- 3) Both partners must self-identify as "in a committed relationship" with their partner for at least 6-months.
 - *Note:* Eligibility will NOT be based on marital/cohabitation status or sexual orientation to remain consistent with VA priorities of offering inclusive family services.
- 4) At least one partner must report at least mild relationship distress on a satisfaction screen (CSI-4<13.5)
- 5) At least one partner must have Veteran status
- 6) The Veteran partner must screen positive on at least one PC-Screen (i.e., PHQ-2 ≥3; PHQi9≥1; AUDIT-C≥5; OR PC-PTSD-5≥4)

List of criteria for exclusion:

- Either partner reports that they are engaged in ongoing couple or family therapy (via brief questions during Telephone Screen).
 Note: Any new couple/family therapy scheduled *after* screening will not impact eligibility and will be evaluated as an outcome.
- 2) Either partner reports severe intimate partner violence in the last year (via semi-structured interview during the Baseline session).
- 3) Either partner reports experiencing suicidal intent / attempts in the last month (via C-SSRS in Baseline session).
 - *Note:* Participants will NOT be excluded based on suicidal ideation or plan alone.
- 4) Either partner experiences current psychosis (via chart review, presentation during session, or MINI psychosis scale).
- 5) Either partner experiences current mania (via chart review, presentation during session, or MINI mania scale).

All staff will be trained in the semi-structured IPV interview, C-SSRS, P4, and MINI psychosis and mania scales to be used at any time they are concerned about individual functioning during either in-person sessions or phone sessions. Veteran charts will be reviewed prior to any Veteran-participants' to check for any indications of hospitalization or records flag. Results will be discussed with Drs. [name] or [name], licensed psychologists who will integrate findings to determine whether exclusion criteria are met.

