5.5 Study Evaluations

Questionnaires

See Table 1 for full list of measures. Except for newly developed measures, all measures have established reliability/validity and were selected with preference for measures used in VHA care.

Inclusion/Exclusion. The listed measures will assess eligibility (per Section 5.4). The relationship quality screen and PC-Screens are established short forms used in VA practice.

Safety. In addition to routine use to evaluate exclusion measures

Outcomes (Aim 2). We selected measures of relationship quality and depression used in weekly assessments for VA EBPs.²⁶ Intimacy and interpersonal risk will be assessed using well-validated measures. We are piloting new measures about communication around mental health.

Evaluation (Aim 3). The well-established acceptability measures are supplemented with open-ended interview questions to identify unique strengths and weaknesses of the program *Risk.* Measures assess shared risk factors for suicide and divorce to contextualize findings.

Table 1List of Measures used in Study										
Construct	Measure	Items	Purpose	Screen	Base	Tx	Post			
Demographics	Standard Items	8	Inclusion	X						
Relationship Status	Made for Study	4	Inclusion	X						
Tx Engagement	Made for Study	6	Exclusion	X						
Veteran Status	Standard Items	5	Inclusion	X						
IPV Assessment	VA IPV Screen	8	Safety		X		Xa			
Severe IPV Behaviors	IPV Interview	8	Exclusion/Safety		(X)	(X)	(X) ^a			
IPV Monitoring	IPV Session	1	Safety			Х				
Mania/Psychosis	MINI ²⁵	20	Exclusion		(X)	(X)	(X)			
Last Month Suicide Ideation Severity	C-SSRS ²⁷	5	Exclusion/ Safety		Х		Х			
Suicide Risk Eval	P4 Screener	4	Safety	(X)	(X)	(X)	(X)			
Relationship Quality	CSI ²⁸	4/32	Aim 2-1	Xb	Х		Х			
Intimacy	PRI	16	Aim 2-1		Х		Х			
Recent (2-Week) Depression	PHQ-9 ²⁹	2/8	Aim 2-2	Xp	Х		Х			
Recent Suicidal Ideation	PHQ-i9 ²⁹	1	Aim 2-2	X	Х		Х			
Last Month Ideation Intensity	C-SSRS ²⁷	5	Aim 2-2		X		Х			
Interpersonal Connection	INQ ³⁰	15	Aim 2-2		X		Х			
Discussing Mental Health	Made for Study	18	Aim 2-3		Х		Х			
Service Utilization	Chart Review	N/A	Aim 2-3				Х			
Perceived Quality of Service	CSQ-18 ³¹	8	Aim 3-1				Xa			
Quality of Alliance w/ Provider	WAI-SR ³²	12	Aim 3-1				Xa			
Semi-Structured Interview	Made for Study	15	Aim 3-2				Х			
Potential PTSD	PC-PTSD-5 ³⁴	6	Inclusion	X						
Trauma Exposure	LEC-5 ³⁵	17	Risk		X					
Childhood Adversity	ACES ³⁶	17	Risk		X					

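### No routine suicidal-ideation question is listed at the treatment sessions, although IPV is asked at every one, and the one-month look-back at Post may not reach back to baseline

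*Combined protocol and SAP*

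**What the plan says.** Section 5.1 (Protections to minimize suicide risk) gives two triggers for the P4 screener: "If participants screen positive for suicidal ideation or researchers become aware that a participant might be thinking about suicide". Under Protection against IPV risk, the same section does not wait for a trigger. Once the separate baseline interviews are done, "all sessions will contain the 1-item self-report IPV screen used as a default in session packets in VA couples therapies".

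Section 5.4 requires the Veteran to be positive on at least one of PHQ-2, PHQi9, AUDIT-C or PC-PTSD-5. Either partner's intent or attempt in the last month excludes the couple, but "Participants will NOT be excluded based on suicidal ideation or plan alone". The risk-benefit text of section 5.1 calls the entry conditions known suicide risk factors, puts participants at somewhat elevated risk of suicidal crises and IPV, and says that discussion in front of a partner may add stress or conflict.

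On timing, section 5.1 says that study activities may finish in one month but "can take up to 3 months from baseline to finish depending on participant scheduling difficulties". The follow-up interview falls within 30 days of the last session, and the referral rule there concerns intent during the preceding month. Sections 5.1 and 5.4 also say that all staff are trained in the C-SSRS and P4 and may use them whenever they are concerned about a participant.

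Section 6.0 counts suicide attempts, new IPV behaviours and occurrences of imminent risk as adverse events.

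**The concern.** The baseline exclusion for recent intent describes a participant only on the day of that interview. Because ideation and plans are admitted, a move from ideation to intent during the course is a foreseeable event. The plan accepts for IPV that one baseline interview does not replace repeated asking, but it lists no equivalent for suicide risk. Sessions may also be held by phone, where staff have fewer cues on which to base a concern.

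Two things are at stake. The first is whether new ideation or intent is noticed before a joint session. The second is statistical: section 5.6 says the exploratory analyses will help judge tolerability and safety for the later RCT, and the trial has no data safety monitoring board. If one kind of event is asked about and the other is only noticed, their counts during treatment cannot be read side by side, and a low suicide-risk count would partly reflect not having asked.

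**Working it through.** The plan gives no figure to reproduce. The check reads Table 1 (section 5.5) by column, compares it with the text, and does arithmetic on the plan's own time windows.

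**Step 1. Schedule in Table 1**

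| Row | Screen | Base | Tx | Post |
|---|---|---|---|---|
| "Last Month Suicide Ideation Severity" (C-SSRS) | | X | | X |
| "Last Month Ideation Intensity" (C-SSRS) | | X | | X |
| C-SSRS lifetime ideation and attempts | | X | | X |
| "Recent Suicidal Ideation" (PHQ-i9) | X | X | | X |
| P4 screener | (X) | (X) | (X) | (X) |
| IPV session item | | | X | |

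The footnotes do not define the brackets. Reading them as *as needed* follows from the conditional wording in section 5.1.

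**Step 2. Which P4 trigger can operate at a session?** With no ideation screen listed under Tx, a positive screen is not available there. What remains is staff awareness, through disclosure or their own concern.

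**Step 3. Count of listed checks**
- Per partner over three sessions: ideation 0, IPV 3.
- Ceiling, if all 20 couples complete: 20 × 2 × 3 = 120 person-sessions.
- At the 75% retention projected in section 5.6: 20 × 0.75 = 15 couples, and 15 × 2 × 3 = 90 person-sessions, plus any attended by couples who later drop out.
- In either case each person-session has a listed IPV item and none has a listed ideation item.

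**Step 4. Look-back at Post.** Time outside the window = time from baseline to interview − one month.
- Shortest course: 1 − 1 = 0 months.
- Longest course: 3 − 1 = 2 months.
- Intermediate case: sessions over 30 days starting just after baseline, interview 30 days after the last one: (30 + 30) − 30 = 30 days.

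The first two lines assume that the interview falls at the end of the stated 1- to 3-month range.

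**Step 5. What the other Post items recover.** Lifetime attempts are asked at both baseline and Post, so a new attempt anywhere in the interval can be found by comparing the two. A lifetime ideation level first endorsed at Post also points to the study period. For someone who already had that level of ideation at baseline, the lifetime item cannot show a recurrence. PHQ-i9 in the Post packet may be completed straight after session 3, which can shorten the stretch without a routine question but does not cover the earlier sessions.

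**The case against.** The best defence is that the plan does not leave suicide risk unattended during treatment. Staff may start a C-SSRS or P4 on their own concern, visible distress has a set response, sessions are recorded, BRC delivery is supervised weekly, and section 5.1 has risk procedures for in-person, phone and video sessions. This stands against any inference that new intent would be found only if volunteered. It does not supply a routine question: training provides the tools, and the mode-specific procedures apply once concern exists.

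A reader might also describe the sample as recruited for suicide risk. The documents do not support that. An alcohol or PTSD screen alone qualifies the Veteran, and supporting partners, half of the person-sessions, need no positive screen.

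Another tempting argument is that the plan contradicts itself because "We selected measures of relationship quality and depression used in weekly assessments for VA EBPs" and yet the depression measure is not given at sessions. That sentence says where the measures come from; it makes no commitment to weekly use in this trial.

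The Intervention Packet (Doc#17) is not in the documents, and Table 1, although called a full list, omits the Relationship Checkup Questionnaire that the packet contains. An ideation item in the packet therefore cannot be ruled out, and the accurate statement is that none is listed.

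Finally, a paper item could do harm if badly delivered. Remote couples receive packets by mail with return envelopes, so a positive answer could lie unread while the session goes ahead. This objection is sound, and it determines how the item should be asked.

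**Conclusion.** The point holds as a gap in ascertainment and is a cheap improvement that should be made. From baseline to the post-treatment assessment, about 1 to 3 months, no routine ideation question is listed at any of the three sessions, while IPV is asked at all three. Detection of new ideation or intent in that time rests on disclosure or staff concern. At Post, ideation with intent is outside the one-month window for about 0 to 2 months of the course; 2 months is the extreme case, not the expected one. Attempts are better covered, so it would be wrong to infer that Post is blind to everything before the last month.

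Suicide-risk and IPV counts during treatment are not comparable as collected. The size of any under-count cannot be calculated, because the documents give no rate of new intent. The conclusion assumes that the brackets in Table 1 mean *as needed* and that the unseen packet holds no ideation item.

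**What to change.** Reconcile Table 1 with the suicide-risk and IPV paragraphs of section 5.1:

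- **At each session:** mark PHQ-i9 with an unconditional X under Tx, answered by each partner separately. For remote sessions, staff should ask it privately at the session contact and not rely only on a mailed form. A positive answer then reaches the P4 step that section 5.1 already contains; that step and the response to it are unchanged. If PHQ-i9 shares the two-week window shown for the PHQ-9 in Table 1, sessions every 1 to 2 weeks would leave little time uncovered.
- **If Doc#17 already has such an item:** correct Table 1 to show it, and confirm how it is asked remotely.
- **Brackets:** define (X) in the footnotes.
- **At Post:** add since-baseline C-SSRS intent and attempt questions for safety reporting, and keep the last-month version for Sub-aim 2-2 so that the pre-post comparison is unaffected.

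The cost is one item already in use per partner per session, a few added questions at Post, and some extra P4 assessments by staff already trained in them. Those extra assessments cannot exceed the 120 person-sessions and would probably fall mostly on participants who enter with ideation; the documents do not give the share.

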5.2 Recruitment Methods

Subject Identification

Potential subjects will be identified and sent a letter through two approaches outlined below in primary care (see letter of support, *Doc#26*) and behavioral health (see letter of support, *Doc#27*). Study personnel will call all patients who receive a letter unless the Veterans opt out by contacting staff and declining participation using the process detailed on the letter. Veterans who wish to initiate the process sooner may also call study staff directly using contact information on the letter.

Letters from providers to patients who have recently screened positive on PC Screens. Outpatient Veterans who have had a positive PC screen (i.e., PHQ-2 ≥3, PHQi9≥1, AUDIT-C≥5, QR PC-PTSD-5≥4) during a past month primary care visit will be identified via monthly data pull by CoE Program Analyst. We are requesting a HIPAA waiver for the data pulls (Doc#4), which will be conducted by an information technologist within VISN 2 or will be requested and extracted from the VA Corporate Data Warehouse (CDW) and placed within VA Informatics and Computing Infrastructure (VINCI). Information will include Veteran Name, Social Security Number, Screen Scores, PCP Name, Phone Number, and Mailing Address. We will do an initial data pull or chart review in the case data pull is delayed due to technical difficulties at the beginning of the study and repeat every month as necessary until enrollment goals are met. This list will then be presented DIRECTLY to the PCP for review and approval. We will then send approved patients the Recruitment Letters from Providers (Doc#13) that describes the study, alerts patients that a member of the research staff will be calling them about the study, and provides ways to opt out of being contacted. We will call the Veteran 1-2 weeks after the date the letter is sent.

Direct provider referral: Referrals for potential participants at each site will come from providers in behavioral health (including suicide prevention coordinators, VA LGBTQ coordinators, IPVAP coordinator) and primary care. VA healthcare providers will be able to refer potentially eligible participants by distributing the same Recruitment Letter (*Doc#13*) and/or Recruitment Flyer (*Doc#32*) directly to the Veteran. Providers may directly hand the letter or flyer to patient, may mail letter to patient, or request that our study team send a letter on their behalf based on clinical judgment and preference. Providers will inform study coordinator that a referral has been made through secure communication. We will call the Veteran 1-2 weeks after the date the provider informs study staff that the referral has been made. [name] (Co-I) also provides couples/family services as part of his clinical responsibilities. In this role, he may receive referrals for Veterans who are potentially eligible for the study. As he typically respond to referrals by reviewing different treatment options with the Veteran, [name] will ask the referring provider if it would be appropriate to include the study as one of the options. If the provider approves, [name] will discuss study with the Veteran. All Veterans will be informed that they can still receive the intervention if they decline to participate in the study.

Screening Process

Veteran screens. Screens will occur by telephone and be conducted by research assistants trained in this procedure; any Veteran may request to be seen in person. During the initial assessment, the research assistant conducting the screening will describe the study and all aspects of consent to the patient and evaluate comprehension of consent using two comprehension questions. Following verbal consent, Veterans will be asked to complete the *Phone Screen Interview Measures (Doc#14)*.

If the Veteran is ineligible to participate in our study or is eligible for other studies, we would like to be able to ask them if they are interested in hearing about other research studies going on at their local VA if they are interested in participating. If interested, we would help connect that participant and the research team with them to obtain additional information.

Supporting partner screens. If a Veteran Partner is eligible and interested, we will request their permission to contact the supporting partner using contact information they provide. We are requesting a *second HIPAA waiver* (*Doc#6*) to request this contact information (Name, Phone Number) from the Veteran partner as it is the only way to feasibly contact the second partner in a way that maximizes their convenience and gives them privacy to accept or decline the study without their partner present. The approach of having the initial partner provide contact information for their partner is standard practice in both longitudinal surveys of couples/families and couples intervention studies in academic medical centers and research universities. It does not require greater disclosure than expected in daily life (e.g., providing partner's information to a gym for a referral bonus; providing partner's contact when scheduling family services), and has not to our knowledge ever resulted in partners from romantic relationships feeling that their privacy has been violated.

Supporting Partner will be scheduled to provide consent and answer questions in a separate screen containing eligibility questions. As a majority of Veterans are in relationships with non-Veterans, we have submitted a Memorandum for Recruitment of Non-Veterans (*Docs#28&29*).

This will provide a separate opportunity to ask questions about the study, screen for intimate partner violence, and provide resources as necessary

Screens Needed. Using previously collected data, we calculated that approximately 40% of Veterans screening positive on PC Screens will be in a current romantic relationship and remain eligible we further expect that approximately 50% of eligible Veterans and 50% of partners would still decline to participate in our study. Thus, to reach our target enrollment of 20 couples, we expect we need to screen 240 participants, or approximately 200 Veterans and 40 partners.

Participant Recruitment Incentives

Participants will receive compensation for their participation in the study. This compensation will be in the form of electronic funds transfer (EFT) or a Direct Express prepaid debit card, per Department of Treasury regulation. For those participants not currently enrolled in EFT or the Direct Express debit card, research staff will inform that participants on the information required for enrollment in EFT or the Direct Express debit card and that the appropriate forms (two copies) were sent to the Veteran participant along with the recruitment letter. Participants may also request that extra copies be sent to their address. Once the Veteran completes the enrollment paperwork, they will be able to send the form to the Canandaigua VA agent cashier.

Each individual participant will be compensated up to \$115 for their participation according to the following schedule:

Phone Screening \$15
Baseline Assessment \$50
Follow-up Assessment (post-treatment) \$50

Note that while this means each couple can earn up to \$230 total, emphasizing separate payments for completion of each study activity by each individual participant ensures participants will be paid for that activity regardless of whether their partner has participated in that activity (e.g., Veterans will be paid for their screen even if they are not enrolled in the larger study due to ineligibility or if their partner subsequently declines their screen). This also serves to maximize confidentiality as study staff will not need to discuss information about a partner's participation in order to resolve an individual's compensation issues.

If there are any issues with enrollment or receipt of compensation, research staff will contact the specific participant over the phone or that participant may call the research staff to communicate about the issues and work toward a resolution. Since this often requires a lot of information to be conveyed over the phone (i.e., research staff contacting the fiscal office for information for the participant) a follow-up letter with this information may also be sent to that participant in order to assist in the resolution of the payment issues. No identifiable data or sensitive payment information will be included with these payment letters.

